The sample size calculations are based on the objective of comparing the serologic response to R21/Matrix-M™ vaccine concurrently given with DHA-PIP + SLD-PQ with R21/Matrix-M™ vaccine alone in adults instead of basing it on safety outcome. This is a Phase II trial. Sample sizes for Phase II trials are usually small, as safety is still of paramount importance. Because of this limitation, these phase II studies are usually powered on the immunogenicity/efficacy endpoints because safety events are rare and a sample size based on safety would lead to a very high sample size that would not be acceptable from ethical standpoint. Another reason why powering it on immunogenicity/efficacy (a co-primary objective) is important, is that if the vaccine has poor immunogenicity profile then the safety question becomes redundant unless the study is a non-inferiority trial. We are optimistic that this sample size will be able to reveal important safety signals between arms which can be further explored in a phase III trial which would be a large trial that may be powered on safety endpoints that are rare. The efficacy endpoint (Immunogenicity objective) is a co-primary objective to the safety objective. We include both “safety” and “immunogenicity” terms in the study title because both of them are key endpoints. Valid sample sizes for comparing sample sizes between two groups are usually obtained using exact test methods such as the Fisher's exact test power calculations. This is done using simulations as sample size formulas are not well developed. To estimate the sample size we use a four-fold increase in anti –CS antibody titre as an assumed correlate of protection. For the sample size calculation, we assume that the background rate of response in the reference groups will be 5% and the true rate of anti-CS antibody response in the vaccine groups is 80%. We wish to exclude, for the vaccine, a one-tailed lower 95% CI for the reference-vaccine group difference of lower than 30%. The study aims to detect this difference with

**Research Proposal Submission Form
for a study involving human subject enrollment WITH
specimen collection**

Document No.: FTM ECF-033-01

Page 12 of 52

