- Serology to quantify and characterise the binding properties of antibodies to the vaccine components (full length R21, CS C-term, NANP and HBsAb), including total IgG, IgG avidity, subclasses and isotypes.
- Functional assays to measure antibody function, such as inhibition of sporozoites invasion and systems serology assays

**Research Proposal Submission Form
for a study involving human subject enrollment WITH
specimen collection**

Document No.: FTM ECF-033-01

Page 27 of 52

- Flow cytometry assays to enumerate and functionally characterise immune cell populations such as effector and memory T cells (e.g. CD4+ and CD8+), T follicular helper cells, regulatory T cells, B cells, plasma cells and dendritic cells
- Enumeration of antibody-secreting cells (e.g. B and plasma cells)
- Assays to assess presence or absence of other factors affecting vaccine immunogenicity, such as antibodies against viral pathogens including cytomegalovirus.
- Other ELISA assays for immunity to malaria that may be relevant to prior malaria exposure and be used to predict vaccine immunogenicity.

Genetic tests for determination of associated genes that can have an impact on vaccination. N.B. Specific consent genetic testing will be sought through an additional question on the ICF to make clear to participants that consent for genetic testing does not affect participation in the clinical trial.

Drug levels

The study investigates two questions regarding the potential interactions between antimalarial drugs and vaccines.

- 1) Does the co-administration of antimalarial drugs with vaccines influence vaccine antibody levels
- 2) Does the co-administration of antimalarial drugs with vaccines influence drug levels.

The second question will be addressed for piperaquine only. Piperaquine levels will be assessed during each round (M0, M1, and M2) on Day 0, 1, 2, and 7 (at M0D0, drug level will be assessed, if additional data are required). (Table 9.) Additional drug level assessment for primaquine will be done if additional data are required.

Table 9. Pharmacokinetic blood sampling time.

Month(s)	Day(s)	PK*
M0	Day 0	x
	Day 1	x
	Day 2	x
	Day 7	x
M1	Day 0	x
	Day 1	x
	Day 2	x
	Day 7	x
M2	Day 0	x
	Day 1	x

**Research Proposal Submission Form
for a study involving human subject enrollment WITH
specimen collection**

Document No.: FTM ECF-033-01

Page 28 of 52

Month(s)	Day(s)	PK*
	Day 2	x
	Day 7	x

Remark:

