* Blood sample will be collected before each dose (at each visit) and then at day 7 for drug levels assessment. The drug levels will be assessed in the 50 participants who receive vaccine and drugs (groups 1) and 20 participants who receive drugs alone (group 3).

B6.6.2 Data Collection and Data Access

Source Data

Source documents are original documents, data, and records from which participants' CRF data are obtained. These include, but are not limited to, hospital records (from which medical history and previous and concurrent medication may be summarized into the CRF), clinical and office charts, registration logbook, laboratory and pharmacy records, diaries, radiographs, referral notes and correspondence. The study staff will derive data from source documents and record it into the volunteers' CRFs, which will be in paper and/or electronic format. This includes safety data, laboratory data (both clinical and immunological) and outcome data.

All documents will be stored safely in confidential conditions. On all study-specific documents, other than the signed consent, the participant will be referred to by a unique study participant number/code, not by name.

Direct access to source data/documents

Direct access to anonymised trial related source data/documents will be granted to authorized representatives from the sponsor, Jenner Institute, Research Ethics Committees (RECs), and the regulatory authorities to permit trial-related monitoring, audits and inspections.

Record Keeping

All study data will be stored under lock and key. The investigators will maintain and retain appropriate medical and research records and essential documents for this trial for a period of 5 years after completion of the study, while electronic data will be retained indefinitely. Only authorized, trained study staff will have access to study records. On all documents, other than the signed consent, the participant will be referred to by the study participant number, not by name.

The principal Investigator will be responsible for data management and for delegating the receiving, entering, cleaning, querying, analysing and storing all data that accrues from the study. Data will be managed and stored in MACRO[®] database, a GCP-compliant electronic data capture system. A study data management plan will outline detailed procedures for data capture, storage, curation and preservation.

**Research Proposal Submission Form
for a study involving human subject enrollment WITH

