specimen collection**

Document No.: FTM ECF-033-01

Page 29 of 52

The investigators will permit authorized representatives of the sponsor, ethical committee(s), regulatory agencies, authorized individuals from, Jenner Institute and the monitors to examine (and when required by applicable law, to copy) clinical records for the purposes of quality assurance reviews, audits and evaluation of the study safety and progress.

B6.7 Data analysis

B6.7.1 Study Endpoints

We will assess the R21/Matrix-M™ recipients with regards to:

Safety: the occurrence of solicited and unsolicited AEs and SAEs (please see safety section)

Immunogenicity: (a) serum anti-CS IgG antibody titres responses to NANP and anti-CS antibody avidity, (b) cellular immunity.

B6.7.2 Inclusion in Analysis

All patients who received at least one dose of vaccine will be included in the safety analyses. Patients lost to follow-up before the completion of the follow-up period assessments will be censored at the last day seen.

B6.7.3 Immunology analyses

Given the incidence of malaria in the study area, it is highly unlikely that any volunteer will become infected with any Plasmodium species during the trial. However, to exclude the remote possibility that a participant becomes infected we will screen participants for malaria at screening, Month 0, Month 1, Month 2, Month 3, and Month 6. Participants positive for malaria at screening or Month 0 are excluded from participation in the study and will not be enrolled or vaccinated.

B6.7.4 Overall plan

Both intention-to-treat and per-protocol analyses will be carried out. In the intention-to-treat analysis, every participant randomized in the study (who receive the correct or incorrect study agent, one or more doses, and complete or incomplete doses) will be analysed, except if he/she did not receive any dose of the study vaccine or if no post-randomization data was collected for this participant.

The per-protocol analysis will compare participants according to the study agent actually received and will include only those participants who satisfied the inclusion/exclusion criteria, followed the protocol, and received three complete, correct doses. The following non-compliant participants will be excluded:

- Participants included without meeting at least one inclusion criterion
- Participants included despite meeting at least one exclusion criterion
- Participants found non-compliant with the blood sampling schedule

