**Research Proposal Submission Form
for a study involving human subject enrollment WITH
specimen collection**

Document No.: FTM ECF-033-01

Page 30 of 52

- Participants vaccinated with the wrong study agent (non-compliance with the randomization code)
- Participants excluded from the intention-to-treat analysis.
- No interim analysis is planned.

B6.7.5 Analysis of baseline characteristics

The demographic characteristics of enrolled participants will be compared by study group.

B6.7.6 Analysis of immunogenicity

The serum anti-CS antibody titre and avidity

The main analyses will involve the serum anti-CS antibody titre and avidity. These parameters will be measured at baseline and then at follow-up times longitudinally. During statistical analysis, we will assess whether a participant had a titre that is greater than 4 times that of the participant's baseline titre. Then we will compute the number of participants who had a titre of greater than 4 times their baseline titres and obtain a proportion of these for each group. These proportions of participants with >4-fold rise in titre from baseline will be compared between arms at each follow-up time. A Fisher's exact test will be used to compare the proportions of participants with >4-fold rise in titre from baseline between groups at each follow-up. These proportions will also be summarised graphically by arm to visually assess the differences between arms over-time. This will help to visually assess whether time modifies the effect of group.

Furthermore, the absolute titre values will be analysed and compared between groups. Since the distribution of these titre values will likely be highly skewed overtime, these values will be log-transformed and compared between arms at the different follow-up times. In order to revert back to the original scale (taking exponentials), the Geometric Mean Ratios (GMR) of the titres will be the measures of effect of interest that will be used to compared the log-transformed titres between the arms. The 95% confidence intervals for the Geometric Mean Ratios will be presented. The mean titre trends (on log-scale) over time will also be plotted by arm to assess whether there is a difference in trends of the titres between arms over time.

Tests of significance will be performed at 5% significance level. Analyses will be performed in Stata version 17 or higher. A separate detailed Statistical Analysis plan will be developed, finalized and signed before databased lock.

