2.1.2 SECONDARY OBJECTIVES

- To compare the immunologic response to R21/Matrix-M™ vaccine when concurrently given with DHA-PIP + SLD-PQ (Arm 1) with R21/Matrix-M™ vaccine alone (Arm 2) in Thai adults.
- To compare the piperaquine levels of participants who received the antimalarial drugs alone (Arm 3) with participants who received the antimalarial drugs combined vaccine (Arm 1).

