2.1.5 SAMPLE SIZE

The sample size calculations are based on the objective of comparing the serologic response to R21/Matrix-M™ vaccine concurrently given with DHA-PIP + SLD-PQ with R21/Matrix-M™ vaccine alone in adults instead of basing it on safety outcome. This is a Phase II trial. Sample sizes for Phase II trials are usually small, as safety is still of paramount importance. Because of this limitation, these phase II studies are usually powered on the immunogenicity/efficacy endpoints because safety events are rare and a sample size based on safety would lead to a very high sample size that would not be acceptable from ethical standpoint. Another reason why powering it on immunogenicity/efficacy (a co-primary objective) is important, is that if the vaccine has a poor immunogenicity profile then the safety question becomes redundant unless the study is a non-inferiority trial. We are optimistic that this sample size will be able to reveal important safety signals between arms which can be further explored in a phase III trial. The efficacy endpoint (Immunogenicity objective) is a co-primary objective to the safety objective. We include both “safety” and “immunogenicity” terms in the study title because both of them are key endpoints. Valid sample sizes for comparing sample sizes between two groups are usually obtained using exact test methods such as the Fisher’s exact test power calculations. This is done using simulations as sample size formulas are not well developed. To estimate the sample size we use a four-fold increase in anti-CS antibody titre as an assumed correlate of protection. For the sample size calculation, we assume that the background rate of response in the reference groups will be 5% and the true rate of anti-CS antibody response in the vaccine groups is 80%. We wish to exclude, for the vaccine, a one-tailed lower 95% CI for the reference-vaccine group difference of lower than 30%. The study aims to detect this difference with at least 90% power (because the detectable difference is big) and testing at 5% significance level. Based on these assumptions and using the method of Blackwelder for precision-based sample size calculations, a total of 20 participants per arm would be needed for arm 3 to test against each of arms 1 and 2 separately because the anticipated difference is too big. However, for arms 1 and 2 (Table 1 below), we will need more participants per group because a smaller detectable effect is anticipated. Using the Fisher’s exact test power simulations, a difference in serologic response of 30% (say 50% vs 80%) gives more than 80% power (i.e. 85% power) with a sample size of 50 participants in each of arms 1 and 2 testing at 5% significance level. Therefore, the total sample size for all the 3 arms will be 120 participants. The size of study groups is relatively small hence it is imperative to minimise potential losses. Whenever possible an attempt will be made to replace study participants should a participant be withdrawn or choose to withdraw. The stata command for obtaining the Fishers exact test power simulations is: power two proportions 0.50 0.80, test(fisher) n1(50) n2(50). This has been performed in Stata 16. The required sample sizes are summarized as follows:

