4.1.4 ANALYSIS POPULATION

Primary outcome analyses will be carried out on both the according to protocol (PP) and the intention to treat (ITT) population. The PP analyses will be the main strategy for the immunogenicity analyses. The safety outcomes will be ITT. In the event of some subjects not meeting the in-/exclusion criteria at baseline being erroneously enrolled in the study, a modified intention to treat analysis (mITT) will be considered. In that case, reasons for exclusions will be clearly documented and justified. In the intention-to-treat analysis, every participant randomized in the study (who receive the correct or incorrect study agent, one or more doses, and complete or incomplete doses) will be analysed, except if he/she did not receive any dose of the study vaccine or if no post-randomization data was collected for this participant.

The per-protocol analysis will compare participants according to the study agent/treatment actually received and will include only those participants who satisfied the inclusion/exclusion criteria, followed the protocol, and received complete, correct doses. The following non-compliant participants will be excluded:

- Participants included without meeting at least one inclusion criterion
- Participants included despite meeting at least one exclusion criterion
- Participants found non-compliant with the blood sampling schedule
- Participants vaccinated with the wrong study agent (non-compliance with the randomization code)
- Participants excluded from the intention-to-treat (mITT) analysis.

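### Read literally, the ITT and PP definitions leave out all of Arm 3; separately, its size of 20 does not follow from the stated Blackwelder inputs, though the gap is conservative

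*SAP*

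**What the plan says.** **Analysis sets.** Protocol B6.7.4 and SAP 4.1.4 share one ITT rule: every randomised participant is analysed "except if he/she did not receive any dose of the study vaccine or if no post-randomization data was collected for this participant". The PP exclusions include, in the protocol, "Participants excluded from the intention-to-treat analysis" and, in the SAP, "Participants excluded from the intention-to-treat (mITT) analysis". The SAP introduces its sets as those for primary outcome analyses; the protocol sets no such limit. Neither document defines a pharmacokinetic set.

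**Safety set.** Protocol B6.7.2 and SAP 3.1 restrict safety to participants who received at least one vaccine dose. SAP section 5 restricts it to those allocated to vaccination. SAP 4.1.4 says that safety outcomes are analysed by ITT.

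**Role of Arm 3.** Table 1 of both documents gives Arm 3 20 participants and no vaccine. SAP 2.1.2, like protocol B2.2, sets the objective "To compare the piperaquine levels of participants who received the antimalarial drugs alone (Arm 3") with those of Arm 1. Protocol B6.6.1 gives the sampling times, "Piperaquine levels will be assessed during each round (M0, M1, and M2) on Day 0, 1, 2, and 7", and the remark to its Table 9 gives the numbers: "The drug levels will be assessed in the 50 participants who receive vaccine and drugs (groups 1) and 20 participants who receive drugs alone". SAP 3.2 lists antibody concentration in all three groups as a primary outcome. The SAP antibody tables have a no-vaccine row, and the safety table has a no-vaccine column.

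**Size of Arm 3.** Protocol B5.3 and SAP 2.1.5 assume a 5% response in the reference group and 80% in the vaccine groups, at least 90% power and a 5% significance level. The criterion is "We wish to exclude, for the vaccine, a one-tailed lower 95% CI for the reference-vaccine group difference of lower than 30" (per cent). Citing Blackwelder's method, they conclude that "a total of 20 participants per arm would be needed for arm 3 to test against each of arms 1 and 2 separately".

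**The concern.** The ITT exception is written as if every arm were a vaccine arm, and the PP rule inherits it. A statistician who applies the definitions as printed has no Arm 3 participant to analyse. That touches the piperaquine objective, for which Arm 3 is the only comparator, and the antibody contrast for which its 20 participants were derived. To run either comparison, someone must depart from the written sets and decide who counts, and nothing requires that decision to be made before the results are seen.

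The sample-size point is one of traceability: a figure attributed to a named method should follow from the stated inputs.

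**Working it through.** **1. Set membership under the printed wording**

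| Arm | n | Planned vaccine doses | In ITT | In PP |
|---|---|---|---|---|
| 1 | 50 | 3 | yes, if dosed | yes, if compliant |
| 2 | 50 | 3 | yes, if dosed | yes, if compliant |
| 3 | 20 | 0 | no | no |

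The excluded share is 20/120 = 16.7%. An Arm 3 participant could enter ITT only by being given vaccine in error, and PP would then exclude that person for receiving the wrong agent.

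**2. Which rule conflicts with which text**

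- *Piperaquine.* The protocol's general sets conflict with B2.2, B6.3.2 and the Table 9 remark. The SAP's sets are tied to primary outcomes, so on its own text the SAP gives this secondary objective no set.
- *Antibody.* SAP 3.2 makes the three-group concentration primary, so SAP 4.1.4 governs it directly and removes Arm 3.
- *Safety.* The received-vaccine rule (SAP 3.1), the allocated-to-vaccine rule (SAP 5) and the ITT rule (SAP 4.1.4) all leave the no-vaccine column of the safety table empty.

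**3. The plan's sample-size figures**

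Arm 1 v Arm 2: Fisher's exact test, 50% v 80%, 50 per arm, has enumerated power 85.3%. The stated 85% reproduces.

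Arm 3, with p0 = 0.05, p1 = 0.80, margin 0.30, one-sided 5% (z = 1.645) and 90% power (z = 1.282):

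n = (z_alpha + z_beta)² × [p0(1 − p0) + p1(1 − p1)] / (p1 − p0 − margin)²

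= (1.645 + 1.282)² × (0.0475 + 0.1600) / (0.45)² = 8.78, so **9 per arm**.

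The stated 20 does not reproduce. Variants:

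| Setting | n per arm |
|---|---|
| One-sided 2.5%, 90% power | 10.77 (11) |
| Continuity-corrected, 90% power, one-sided 5% / 2.5% | 13 / 15 |
| 95% power, one-sided 5% / 2.5% | 11.09 / 13.32 (12 / 14) |
| 99% power, one-sided 5% / 2.5% | 16.16 / 18.83 (17 / 19) |
| Pooled variance, one-sided 5%, 90% power | 20.67 |

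With 2.5:1 allocation at 90% power, Arm 3 would need 5 (one-sided 5%) or 6 (2.5%). Some settings come near 20, but the documents do not say that any of them was used.

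**4. Exact power for the stated antibody contrast**

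Full binomial enumeration, one-sided 5%, lower limit above 30 points:

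| Vaccine v Arm 3 | Wald | Score |
|---|---|---|
| 9 v 9 | 82.5% | 82.5% |
| 20 v 20 | 98.4% | 98.1% |
| 50 v 20 | 99.9% | 99.8% |

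**5. What 50 v 20 can deliver for piperaquine**

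The documents give no coefficient of variation (CV), so the CV here is an assumption. For one time point, the 95% CI of the Arm 1/Arm 3 geometric mean ratio is the estimate multiplied and divided by

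exp(1.96 × √ln(1 + CV²) × √(1/50 + 1/20)),

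which is 1.16, 1.22, 1.28 and 1.33 at CV 30, 40, 50 and 60%.

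**The case against.** **The intent is clear.** The objective, the Table 9 remark and the no-vaccine rows and columns all show that Arm 3 is to be analysed, and no sensible analyst would report 50 participants against none. This stands as to intent. A reader might infer that the trial plans to drop Arm 3, or that the comparison will really be 50 v 0; the documents support neither. What remains is a general rule that contradicts the specific text around it.

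**The SAP sets cover primary outcomes only.** This also stands. A reader might infer that SAP 4.1.4 itself removes Arm 3 from the piperaquine comparison; its opening sentence does not support that. The protocol's unrestricted sets do conflict, and in the SAP the rule bears instead on the three-group antibody outcome.

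**Piperaquine is not left without any analysis.** SAP 4.1.6 promises descriptive statistics for each study measure, by randomised group and time point, and the sampling schedule is complete. It would be too strong to say that nothing is planned. The missing items are an exposure measure, a comparison method and an analysis set. The first two are missing detail; the set is the contradiction.

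**Twenty is safe.** It is, because the requirement is at least 90% power. A reader might infer from the formula that Arm 3 is more than twice the necessary size and could be cut to 9. The documents do not support that: they ask for at least 90% power and favour exact methods, and exact power at 9 v 9 is only 82.5%.

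**Conclusion.** The main point holds as a literal contradiction. As worded, the ITT and PP rules exclude every Arm 3 participant treated as assigned, while both documents require Arm 3 for piperaquine and the SAP also requires it for antibody and safety tables. This rests only on Arm 3 receiving no vaccine, which both documents state. It should be corrected, since it affects the sole comparator for one of the two secondary objectives.

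The sample-size point is minor. The stated inputs give 9 rather than 20, but 20 exceeds every Blackwelder variant tried at 90% power with unpooled variance, so no antibody conclusion is put at risk. The power figures assume the documents' 5% and 80% response rates.

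A related inconsistency concerns the antibody endpoint itself. SAP 3.2 makes it primary, in all three groups, at Months 1 and 2. Protocol B6.3.2 makes it secondary, in Arms 1 and 2, at Months 1, 2, 3 and 6. The protocol therefore sizes Arm 3 for an antibody contrast that its own endpoint list does not include.

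**What to change.** 1. **ITT and PP (protocol B6.7.4, SAP 4.1.4).** Replace the reference to a dose of the study vaccine with *any dose of any study agent (vaccine or antimalarial)*. Do not write *allocated* agent: the same sentence keeps participants who received an incorrect agent. In PP, let complete and correct doses mean those of the assigned regimen.
2. **Piperaquine (both documents).** Define the set as Arm 1 and Arm 3 participants with at least one DHA-PIP dose and at least one later level. Report the Arm 1/Arm 3 geometric mean ratio with its 95% CI from the samples already scheduled. The exposure measure and model can be left to the sponsor's statistician. Label any CV used for expected precision as an assumption.
3. **Safety (protocol B6.7.2; SAP 3.1, 4.1.4, 5).** State one rule: either safety is limited to vaccine recipients, or it includes the no-vaccine column. Because SAP 4.1.4 makes safety ITT, change 1 would bring Arm 3 in, so these sections must change together.
4. **Sample size (protocol B5.3, SAP 2.1.5).** Keep 20. Replace the statement that it is the Blackwelder requirement with its actual basis. If none is on record, give the exact power: about 98% at 20 v 20 and above 99% at 50 v 20. Do not print 9 as the requirement.
5. **Antibody endpoint.** Reconcile SAP 3.2 with protocol B6.3.2 on status, arms and time points.

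The cost is text edits in both documents, with approval of the protocol amendment where required, and one comparison of samples already planned. Enrolment and sampling stay as they are. The edits should be in place before database lock, by which time protocol B6.7.6 already requires a signed SAP.
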